**** Protocol:**

Prophylaxis: Administer gammaCore® Sapphire daily, prophylactically, scheduled three times a day (morning, mid-day and 1 hour before bed at night). One treatment is defined as 2 consecutive doses (stimulations). Each dose delivers a 2-minute stimulation. One dose is applied to the left side of the neck, then one is applied to the right. This would be a total of 6 treatments (2 stimulations x 3 times per day).

For acute respiratory distress or shortness of breath (SOB): Administer one treatment of gammaCore® for acute treatment of shortness of breath (as needed, up to nine times a day). One treatment is defined as 2 consecutive doses (stimulations). Each dose delivers a 2-minute stimulation. One dose (stimulation) is applied to the left side of the neck, then one to the right. If shortness of breath (SOB) persists 20 minutes after start of first treatment, administer a second treatment. If the additional treatments do not appear to be providing benefit/relief of symptoms (as per patient or physician discretion) there is no need to continue with additional acute treatments. However, if it there appears to be benefit, the patient can administer more as needed. The patients can receive up to 9 acute treatments (or 18 stimulations) per day.

Determination of benefit/relief of symptoms will be determined collaboratively between patient and a research investigator who is caring for the patient. Should the acute treatments not provide any relief, the research investigator will determine if/what standard of care therapies are necessary, to treat symptoms. If patient remains in stable condition, they can continue with prophylactic treatments (3xday), when/if possible. Once symptoms are treated (standard of care) and patient is stable again, they can resume the acute treatments (up to 9x day) and continue with this process, until study completion (until they are placed on mechanical ventilation, are discharged, or can no longer continue with treatments, per patient or physician discretion/withdrawal from study).

The devices are pre-programmed to not allow more than 30 stimulations in a 24 hour period. This is a safeguard with the device that cannot be changed. Once the maximum daily number of treatments has been reached, the device will not deliver any more stimulations until the following 24-hour period. (The stimulation automatically stops 120 seconds after the device is powered on).

[†] Frozen blood sample - Cryopreserved leukocytes will be used in future studies, under peer-reviewed funding support, to determine changes in leukocytes not measured during this trial (e.g. Tregs, Bregs, dendritic cells) as well as transcriptomes (RNA-Seq) and epigenotypes.

7.2.1.2 Days 1 – 3

For days 1 through 3, the following assessments will be recorded each day:

- Study Measurements
 - Height/Wt, BMI
 - Temperature
 - Blood Pressure
 - O₂ Saturation
 - PaO₂/FiO₂ ratio
 - Shortness of Breath (Yes / No)
 - Cough (Yes / No)
- Labs to be drawn early am (**before 10 am**) on odd days only

- Immunokine panel, specifically TNF- α , IL-1 β , IL-6
- Frozen blood sample
- Leukocyte flow cytometry
- Pro-Calcitonin
- C-reactive protein
- Ferritin
- D-Dimer
- CBC with differential
- Comprehensive metabolic panel ***Day 3 only** (then drawn on all odd days)*
- VNS Stimulation supervised
 - Total number of gammaCore[®] treatments administered
 - Date and times of stimulations
- Daily Tx Log (Oxygen dependence & data, ventilator dependence & data, discharge data, survival)
 - Oxygen Required (Yes / No)
 - Oxygen level (%) based on device type (HFNC / NC / Bipap / Optiflow)
 - Ventilator Dependence (Yes / No)
 - Date and time of Ventilation
 - Patient discharge home (Yes / No)
 - Date and time (in 24 hour format) of Discharge
 - Survival (Yes / No)
- Clinical Improvement Scale
 - Concomitant medication assessment
 - Adverse event assessment

7.2.1.3 All Even Days Starting Day 4

For all days starting on day 4, lab work is not required, only the following assessments will be recorded each day:

- Study Measurements
 - Temperature
 - Blood Pressure

- O₂ Saturation
- Shortness of Breath (Yes / No)
- Cough (Yes/No)
- nVNS stimulations
 - Total number of gammaCore® treatments administered
 - Date and times of stimulations
- Daily Tx Log
 - Oxygen Required (Yes / No)
 - Oxygen level (%) based on device type (HFNC / NC / Bipap / Optiflow)
 - Ventilator Dependence (Yes / No)
 - Date and time of Ventilation
 - Patient discharge home (Yes / No)
 - Date and time (in 24 hour format) of Discharge
 - Survival (Yes / No)
- Clinical Improvement Scale
- Concomitant medication assessment
- Adverse event assessment

7.2.1.4 All Odd Days Starting Day 5

For all odd days starting on day 5, the following assessments will be recorded each day:

- Study Measurements
- Labs to be drawn early am (**before 10 am**)
 - Immunokine panel, specifically TNF-α, IL-1β, IL-6
 - Frozen blood sample
 - Leukocyte flow cytometry
 - Pro-Calcitonin
 - C-reactive protein
 - Ferritin

- D-Dimer
 - CBC with differential
 - Comprehensive metabolic panel
- nVNS stimulations
 - Total number of gammaCore® treatments administered
 - Date and times of stimulations
- Daily Tx Log
 - Oxygen Required (Yes / No)
 - Oxygen level (%) based on device type (HFNC / NC / Bipap / Optiflow)
 - Ventilator Dependence (Yes / No)
 - Date and time of Ventilation
 - Patient discharge home (Yes / No)
 - Date and time (in 24 hour format) of Discharge
 - Survival (Yes / No)
- Clinical Improvement Scale
- Concomitant medications
- Adverse event assessment

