1 SYNOPSIS

CLINICAL INVESTIGATION TITLE: A Prospective, Randomized, Controlled Study Assessing Vagus Nerve Stimulation in CoViD-19 Respiratory Symptoms (SAVIOR II)

CLINICAL INVESTIGATION CODE:

2020-132-AGH

CLINICAL INVESTIGATIONAL MEDICAL DEVICE(S):

gammaCore Sapphire® (non-invasive vagus nerve stimulator)

OBJECTIVES:

The aims of this study are to summarize and compare the incidence of clinical events and pro-inflammatory cytokine levels in patients randomized to use of gammaCore Sapphire plus standard of care vs standard of care alone in patients hospitalized for CoViD-19. In addition, this study is intended to demonstrate the safety of gammaCore Sapphire use in patients hospitalized for CoViD-19.

Specific clinical events to be summarized include, but are not limited to:

- Changes in oxygen support requirements (no oxygen support, low-flow oxygen support, nasal high-flow oxygen support, noninvasive mechanical ventilation, and invasive mechanical ventilation)
- Changes in O₂ saturation
- PaO₂/FiO₂ ratio
- Proportion of subjects requiring mechanical ventilation
- Days to onset of mechanical ventilation
- Live discharge from the hospital
- Patient length of stay
- Mortality
- Shortness of Breath
- Clinical improvement Scale

Specific laboratory measurements to be summarized include, but are not limited to:

- TNF- α
- IL-1 β
- IL-6
- CRP
- Ferritin
- D Dimer

- Pro-Calcitonin

OVERALL CLINICAL INVESTIGATION DESIGN:

The study is a prospective, randomized, controlled investigation designed for comparison of two groups for the reduction of respiratory distress in a CoViD-19 population, using gammaCore Sapphire® (nVNS) plus standard of care (active) vs. standard of care alone (SoC), the control group. The gammaCore® (nVNS) treatments will be used acutely and prophylactically.

Prophylactic

Administer one treatment of gammaCore®, scheduled three times a day (morning, mid-day and 1 hour before bed at night)

One treatment is defined as 2 consecutive doses (stimulations). Each dose delivers a 2-minute stimulation. One dose is applied to the left side of the neck, then one is applied to the right side

SoC: No Administration of gammaCore®

AND

Acute respiratory failure (w/hypoxia) or Shortness of breath

Administer one treatment of gammaCore® for acute treatment of shortness of breath (as needed, up to nine times a day)

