Treatment paradigms have been developed and tested in clinical trials to support FDA clearance for the acute treatment of pain associated with episodic cluster and migraine headaches, and the prevention of cluster and migraine headache. This experience demonstrates that nVNS may be administered safely in up to 24 two-minute doses (stimulations) per day. We thus have data to draw on as to how to effectively stimulate the vagus nerve. Given the multiple modes of action with blocking the CAP, and acute bronchodilatation, using a similar treatment paradigm for a trial to evaluate nVNS treatment of ARDS is reasonable. The device should be used both prophylactically and acutely early in the course of the disease prior to mechanical ventilation, and once trained, treatment can be fully managed by either a healthcare professional or the patient. If one waits until mechanical ventilation has started, it is less likely that a therapy will be able to block the cytokine storm and outcomes will be less profound.

With respect to the theoretical cardiac and respiratory side effects of non-invasive treatment, historically, stimulation of the vagus nerve is associated with adverse side effects, including bradycardia and bronchoconstriction. These effects were shown to be the result of indiscriminant stimulation of all fibers in the vagal bundle (the vagus nerve is primarily comprised of A and C fibers), which could be avoided by specifically tuning the electrical signals to selectively stimulate only the A fibers. This is possible because of the difference in electric field strengths necessary to activate the different fiber types.³⁴

The intensity, pulse duration and frequency of gammaCore® (nVNS) stimulation parameters have been optimized to induce signals in the large, myelinated A β fibers of the cervical branch of the vagus nerve. Since gammaCore® activates only the low threshold afferent A β fibers, versus the high threshold efferent C-fibers that innervate the heart, there is no known risk for adverse cardiac or other systemic parasympathetic effects.

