electroCore has conducted pre-clinical studies to assess the potential risk of vagus nerve overstimulation on the heart and airways. Several studies were conducted in beagle dogs with hypersensitized airways (worst case for airway reactivity) at maximum stimulation output for 2 minutes. Review of heart rate and airway resistance before, during and after stimulation indicated that there were no significant adverse changes associated with stimulation.³⁷ These results are consistent with the human clinical experience with the gammaCore® device. Regarding the theorized mechanism of action, afferent fibers from the vagus nerve enter the brain and synapse onto the nucleus tractus solitarius (NTS) in the brain stem¹, making connections with many structures in the brain including the locus coeruleus (LC), the periaqueductal gray (PAG) and the raphe nucleus (RN).³⁵ These structures are known to control the release of key inhibitory neurotransmitters. Numerous animal and clinical studies over the last 25 years have implicated the activity of these structures, in particular the LC, in the mechanism of action of VNS to inhibit seizures.³⁶

Clinical Use for Clinical Care

Given the lack of other effective and/or reasonable options for a patient with CoViD-19 respiratory distress and the anticipated demands on our healthcare system, considering gammaCore® (nVNS) therapy, we propose, is a reasonable approach. To achieve goal of decreasing health care burden with patient benefit of decreasing ventilator dependency, inflammatory response and mortality, plan to use it early in course of disease i.e. prior to severe respiratory distress and the need for mechanical ventilation.

The presumptive mechanisms of bronchodilatation and modulation of the cytokine storm would suggest that early intervention is ideal in improving pulmonary function and avoiding respiratory depression.

- 1) Prevention. Mitigation of pro-inflammatory immunokine release would be best achieved with two doses (stimulations), consisting of a two-minute stimulation, on each side of the neck three times a day (am, afternoon and an hour before bed). This would be a total of 6 treatments (2 stimulations x 3 times per day) of stimulation as a prophylactic/preventive measure. This dosage is well below the known safety dosage threshold.

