- 2) In addition, patients may receive additional treatments when experiencing acute respiratory distress. Similarly, one treatment is two doses (stimulations). Each treatment (consisting of two-minute stimulation on each side) is performed on the neck. If shortness of breath (SOB) persists 20 minutes after start of first treatment, administer a second treatment. Maximum number of acute treatments per day is 9. This is symptomatic control and can be used to improve FEV₁, Work of Breathing or dyspnea.

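### The prophylaxis instruction totals the day at 6 treatments, but its own definition and schedule give 3 treatments (6 stimulations)

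*Combined protocol and SAP*

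**What the plan says.** The prophylaxis paragraph appears under the Protocol note in the Synopsis and again in Section 7.2.1.1. It names three times of day, gives the unit ("One treatment is defined as 2 consecutive doses (stimulations")), and closes with the total "This would be a total of 6 treatments (2 stimulations x 3 times per day"). Section 5.1 (Clinical Use for Clinical Care) repeats it: "This would be a total of 6 treatments (2 stimulations x 3 times per day) of stimulation as a prophylactic/preventive measure".

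Other places count three a day:

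- The design summary in the Synopsis: "Administer one treatment of gammaCore®, scheduled three times a day".
- Section 7.2.1.1, on patients whose acute treatments bring no relief: "they can continue with prophylactic treatments (3xday), when/if possible".
- Table 1 (Section 7.2.2), which lists stimulation as three times plus as needed.

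For acute use the same unit is applied consistently: "The patients can receive up to 9 acute treatments (or 18 stimulations) per day". Section 5.1 agrees on the count: "Maximum number of acute treatments per day is 9".

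Two other daily figures bear on the point. Section 5.1 says of the headache trials: "This experience demonstrates that nVNS may be administered safely in up to 24 two-minute doses (stimulations) per day". Sections 7.2.1.1 and 7.5.1 put the device's built-in cap at 30 stimulations in 24 hours.

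**The concern.** One paragraph gives a unit, a schedule and a total, and the total does not follow from the other two. The next paragraph uses the unit correctly, so a reader who applies it consistently would double the scheduled amount.

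The sentence sits in the operative instruction. Section 7.2.1.1 says patients are told to follow the protocol and that it will be kept at the bedside, and Section 7.6 has patients treat themselves unless they cannot do so safely. What is at stake is whether staff and patients work to one scheduled amount, and whether the daily count on the form can be interpreted.

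The units drift elsewhere too. The visit lists in the Synopsis and in Sections 7.2.1.2 to 7.2.1.5 record a daily number of treatments, while footnote c of Table 1 records a number of doses. An entry of 6 could therefore mean 6 or 12 stimulations.

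**Working it through.** Inputs, all from the documents:

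- stimulations per treatment: 2 (Synopsis; Section 7.2.1.1)
- scheduled occasions per day: 3 (same places)
- treatments per occasion: 1 (Synopsis)
- acute maximum: 9 treatments per day (Section 7.2.1.1; Section 5.1)
- earlier experience cited: up to 24 stimulations per day (Section 5.1)
- device cap: more than 30 stimulations in 24 hours is blocked (Section 7.2.1.1)

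**The plan's own figure.** The bracket gives 2 stimulations × 3 = 6 stimulations. The number 6 reproduces only in that unit. In treatments the schedule is 3 × 1 = 3. Check: 3 treatments × 2 = 6 stimulations.

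**The printed total at the defined unit.** 6 treatments × 2 = 12 stimulations, and 12 / 6 = 2.

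**Acute allowance.** 9 × 2 = 18 stimulations, which matches the plan's own conversion.

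**Daily totals** when *a* acute treatments are used:

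| Acute treatments (*a*) | Schedule as defined: 6 + 2*a* | 6 treatments at the defined unit: 12 + 2*a* |
|---|---|---|
| 0 | 6 | 12 |
| 6 | 18 | 24 |
| 7 | 20 | 26 |
| 9 | 24 | 30 |

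**Against the 24 cited in Section 5.1.** 12 + 2*a* exceeds 24 only when *a* is greater than 6. At the full allowance the excess is 30 − 24 = 6 stimulations, and 6 / 24 = 25%. Scheduled use alone (6 or 12) stays below 24 on either reading.

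**Against the device cap.** 30 is not more than 30, so the device would deliver it.

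**The case against.** The case for treating this as a slip of the pen is strong. The sentence shows its own working in the bracket. Three times of day are named, with one stimulation on each side of the neck, and no passage gives times for six prophylactic sessions. Training also reduces the risk: the first treatment is supervised, re-training is available, and a trained investigator transcribes the log daily (Section 7.2.1.1). Section 7.10.4 reports only minor protocol deviations among the first 20 patients to complete. All of this stands and limits the consequence. It does not make the total correct.

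A reader might infer more than the documents support:

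- **That the plan prescribes 30 stimulations a day, or breaks its own limit of 24.** No section states a combined daily maximum for this trial. The 24 in the table is derived as 6 + 18; the 24 in Section 5.1 describes earlier experience. Reaching 30 needs both a misreading of the sentence and use of the full acute allowance.
- **That the device cap was meant to enforce the schedule and fails to.** It is described as a fixed device safeguard. All that follows is that it would not stop a total of 30.
- **That bedside material carries the error.** The bedside copy is not among the documents, so this is unknown.
- **That the per-protocol set would be distorted.** Section 7.10.1.1 excludes patients who depart from prescribed use more than 33% of the time. If adherence were counted in treatments, 3 a day would be 0% missed against 3 and 1 − 3/6 = 50% missed against 6. But the section does not say how adherence is counted, so this is only a possibility.

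The effect on planned analyses is small in any case. Times of stimulations are recorded, exposure is summarised in days (Section 7.10.1.5), and comparisons between arms are not inferential (Section 7.10.1.2).

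**Conclusion.** The stated prophylactic total is wrong under the documents' own definition, by a factor of two in the unit: 6 treatments are printed where the schedule gives 3 treatments, or 6 stimulations. The same error stands in three places and conflicts with three others. The likeliest cause is that treatments was written for stimulations, but that is an inference from the bracket and only the sponsor and investigator can confirm the intended amount.

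The practical size is conditional. Taken at the defined unit, the scheduled amount is 12 stimulations rather than 6, and the largest possible day is 30 rather than 24. The excess over the 24 cited from experience arises only from the seventh acute treatment onwards. The conclusion rests on one treatment per scheduled occasion, as the Synopsis states. It should be corrected because it sits in a self-administered treatment instruction and costs little to put right, not because it threatens the trial's results.

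**What to change.** The sponsor and investigator should reconcile the design summary and Protocol note in the Synopsis, Section 5.1 (Clinical Use for Clinical Care), Section 7.2.1.1 and Table 1 to one confirmed scheduled daily amount, stated in both treatments and stimulations. Which amount is intended is for them to say.

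The recorded daily count should use one unit throughout: the visit lists and footnote c of Table 1 should name the same one. Adding a doses label to an item still called treatments would repeat the mix-up. Any bedside copy of the instruction should be checked against the reconciled text.

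Cost: a numbered wording amendment with justification and IRB agreement, as Section 7.11 requires. It adds no patients, visits, procedures or analyses.

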7.2.1.5 Day of Study Completion

The last day of the study will be determined by discharge, transition to mechanical ventilation and/or if the patient is unable to continue. The following will be recorded:

- Study Measurements
 - Height/Wt, BMI
 - Temperature
 - Blood Pressure
 - O₂ Saturation
 - PaO₂/FiO₂ ratio
 - Shortness of Breath (Yes / No)
 - Cough (Yes / No)
- Labs
 - Pro-Calcitonin
 - C-reactive protein

Clinical Investigation Plan

- Ferritin
- D Dimer
- CBC with differential
- Comprehensive metabolic panel
- nVNS stimulations
 - Total number of gammaCore® treatments administered
 - Date and time of stimulations
- Daily Tx Log
 - Oxygen Required (Yes / No)
 - Oxygen level (%) based on device type (HFNC / NC / Bipap / Optiflow)
 - Ventilator Dependence (Yes / No)
 - Date and time of Ventilation
 - Patient discharge home (Yes / No)
 - Date and time (in 24 hour format) of Discharge
 - Survival (Yes / No) with Date and Time of Death
- Clinical Improvement Scale
 - Concomitant medication assessment
 - Adverse event assessment

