 - Total number of gammaCore® treatments administered with Date/time
- Daily Tx Log
 - Oxygen Requirements, Oxygen level (%), Ventilator Dependence, Date and time of Ventilation, Patient discharge home, (if applicable) Date and time of Discharge, Survival
- Clinical Improvement Ordinal Scale
- Concomitant medication and adverse event assessments

All Odd Days Starting Day 5

Same as Days 1 and 3

Study Completion

The last day of the study will be determined by discharge, transition to mechanical ventilation and/or if the patient is unable to continue i.e. death or feasibility impossible. The following will be recorded:

- Study Measurements:
 - Height/Wt, BMI, Temperature, Blood Pressure, O₂ Saturation, PaO₂/FiO₂ ratio, Shortness of Breath, Cough
- Labs (Standard of care)
 - Pro-Calcitonin, C-reactive protein, Ferritin, D-Dimer, CBC with differential,

Comprehensive metabolic panel

- Labs (Research) Early am blood draw (before 10 am)
 - TNF- α , IL-1 β , IL-6
- VNS stimulations
 - Total number of gammaCore® treatments administered, dates/times
- Daily Tx Log
 - Oxygen Required, Oxygen level (%) based on device type (HFNC / NC / Bipap / Optiflow), Ventilator Dependence (Yes / No), Date and time of Ventilation, Patient discharge home (Yes / No), Date and time (in 24 hour format) of Discharge, Survival (Yes / No) with Date and Time of Death
- Clinical Improvement Ordinal Scale
 - Concomitant medication and adverse events assessment

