6 CLINICAL INVESTIGATION OBJECTIVES

The aims of this study are to summarize and compare the incidence of clinical events and pro-inflammatory cytokine levels in patients randomized to use of gammaCore Sapphire plus standard of care vs standard of care alone in patients hospitalized for CoViD-19. In addition, this study is intended to demonstrate the safety of gammaCore Sapphire use in patients hospitalized for CoViD-19.

Specific clinical events to be summarized include, but are not limited to:

- Changes in oxygen support requirements (no oxygen support, low-flow oxygen support, nasal high-flow oxygen support, noninvasive mechanical ventilation, and invasive mechanical ventilation)
- Changes in O₂ saturation
- PaO₂/FiO₂ ratio
- Proportion of subjects requiring mechanical ventilation
- Days to onset of mechanical ventilation
- Live discharge from the hospital
- Patient length of stay
- Mortality
- Shortness of Breath
- Clinical improvement Scale

Specific laboratory measurements to be summarized include, but are not limited to:

[figure not shown]
- TNF- α
- IL-1 β
- IL-6
- CRP
- Ferritin
- D Dimer
- Pro-Calcitonin

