7.2 Clinical Investigation Procedures and Definitions

Once the patient is admitted to the hospital, the institution shall follow their standard protocol for their CoVid-19 patients. The investigator shall administer the consent form, conduct the intake and randomize the patient 1:1 into each of the two study arms prior to baseline measurements. Once qualified, the patient shall be trained on the use of gammaCore® and provided an initial treatment. For every day the patient is in the hospital but not on mechanical ventilation, the administration of gammaCore®, prophylactically and acutely, will be recorded on the daily study log as per protocol treatment.

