7.2.2 Clinical Investigation Flow Chart

Procedures and outcome measures will be collected as described in the clinical investigation flow chart shown in Table 1.

Table 1 Clinical Investigation Flow Chart

Protocol requirements	Study Visit (D=Day)								
	Admission/ D0	D1	D2	D3	D4	D5	D6	D7	Study Termination ^e
Informed Consent	X								
Inclusion/ Exclusion criteria	X								
Randomization	X								
Complete physical exam	X								
Enter Device #	X								
Intake ^a	X								
Study Measurements ^b	X	X	X	X	X	X	X	X	X
Pro-Calcitonin, C-reactive protein, ferritin, D-dimer, CBC w/dif	X (+ serum/urine hCG for women who may be pregnant)	X		X		X		X	X
Comprehensive metabolic panel	X			X		X		X	X
Study labs drawn before 10am (Frozen blood sample, Immunokine panel (Luminex) including (TNF- α , IL-1 β , IL-6), Leukocyte flow cytometry		X	X	X		X		X	

Clinical Investigation Plan

	Study Visit (D=Day)									
Protocol requirements	Admission/ D0	D1	D2	D3	D4	D5	D6	D7	Study Termination ^e	
Device training ^c	X									
nVNS Stimulation Supervised ^c	X	X								
VNS Stimulation ^c		3X +prn	X							
Clinical Improvement Scale	X	X	X	X	X	X	X	X	X	
Daily Tx Log completed ^d	X	X	X	X	X	X	X	X	X	
Concomitant medications	X	X	X	X	X	X	X	X	X	
Adverse Event	X	X	X	X	X	X	X	X	X	

- ^a Includes collection of basic demographics (DOB, Race, Sex, Smoking Status, County/Region), medications, comorbidities CoViD-19 test results)
- ^b Includes height/weight (BMI), temperature, blood pressure, O₂ saturation, PaO₂/FiO₂ ratio, shortness of breath assessment, cough assessment
- ^c For the active study arm. Includes record of treatment (time and number of doses administered)
- ^d The following parameters will be recorded daily: Oxygen dependence & data, ventilator dependence & data, discharge data, survival, device treatment record (active study arm only)
- ^e Study completion will be determined by discharge, transition to mechanical ventilation and/or if the patient is unable to continue

7.3 Discussion and Justification of Clinical Investigation Design, Including the Choice of Control Groups

The study design (randomized, including a control group) was chosen to evaluate the usefulness of the gammaCore® Sapphire device for symptom improvement in patients suffering CoViD-19 related respiratory distress compared to standardized institution treatment only.

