7.7.2 Objectives

The aims of this study are to summarize and compare the incidence of clinical events and pro-inflammatory cytokine levels in patients randomized to use of gammaCore Sapphire plus standard of care vs standard of care alone in patients hospitalized for CoViD-19. In addition, this study is intended to demonstrate the safety of gammaCore Sapphire use in patients hospitalized for CoViD-19.

Specific clinical events to be summarized include, but are not limited to:

- Changes in oxygen support requirements (no oxygen support, low-flow oxygen support, nasal high-flow oxygen support, noninvasive mechanical ventilation, and invasive mechanical ventilation)
- Changes in O₂ saturation
- PaO₂/FiO₂ ratio
- Proportion of subjects requiring mechanical ventilation
- Days to onset of mechanical ventilation
- Live discharge from the hospital
- Patient length of stay
- Mortality
- Shortness of Breath
- Clinical improvement Scale

Specific laboratory measurements to be summarized include, but are not limited to:

- TNF- α
- IL-1 β
- IL-6
- CRP
- Ferritin
- D Dimer
- Pro-Calcitonin
-

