7.7.5 Appropriateness of Measurements

The evaluative measurements include changes in oxygen support, O2 saturation and shortness of breath, the need and onset of mechanical ventilation, clinical improvement assessment and mortality. We will also correlate these with cytokine suppression. It is possible that those who have a drop, or do not have an increase in cytokine activation will have a higher survival and lower need for oxygen requirements and/or mechanical ventilation. These will permit evaluation of the objectives for the study.

The safety measurements are typical for a clinical trial and permit evaluation of the safety of the device.

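### The study record ends at mechanical ventilation, so live discharge and length of stay, and possibly mortality, are incomplete for ventilated patients

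*Combined protocol and SAP*

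**What the plan says.** Four places make ventilation the end of a patient's study:

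- Section 7.2.1.5: "The last day of the study will be determined by discharge, transition to mechanical ventilation and/or if the patient is unable to continue".
- Synopsis, Study Completion: "transition to mechanical ventilation and/or if the patient is unable to continue i.e. death or feasibility impossible".
- Section 7.2.1.1, device protocol: treatment continues "until study completion (until they are placed on mechanical ventilation, are discharged, or can no longer continue with treatments".
- Table 1, footnote e: "Study completion will be determined by discharge, transition to mechanical ventilation and/or if the patient is unable to continue".

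Survival, discharge and ventilator status are recorded in the Daily Tx Log (Table 1, footnote d). Its last entry is made on the day of study completion, and the last column of Table 1 is Study Termination. No visit, call or chart review is scheduled after it.

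The listed outcomes reach further. The synopsis and Sections 6 and 7.7.2 name mortality, "Live discharge from the hospital" and "Patient length of stay" among the events to be summarised and compared, with no time horizon. Section 7.7.5 names as evaluative measures "the need and onset of mechanical ventilation, clinical improvement assessment and mortality". Section 7.6 gives fewer hospital days as an anticipated benefit.

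**The concern.** For a patient whose study ends at ventilation, the closing log entry cannot show how the admission ended. A later live discharge is not counted, a later death may not be, and length of stay stops at the ventilation date if it is taken from the study record.

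This is not neutral between arms. Section 5.1 hypothesises less ventilator dependence, and Section 7.6 lists avoiding ventilation as a benefit. If the device changes how many patients are ventilated, it also changes how many outcomes are cut short in each arm. Descriptive summaries are distorted in the same way as formal tests would be. The same section also hopes to free patients from ventilation sooner, which a record that stops at ventilation cannot show.

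The incidence and timing of ventilation, and oxygen and laboratory data up to that point, are captured and not in question.

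**Working it through.** The plan gives no figure to reproduce: there is no ventilation rate, event rate or power calculation. The check therefore has two parts.

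**1. Does any other provision close the gap?**

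| Provision | What it reaches | What it leaves open |
|---|---|---|
| 7.8.5, reporting to the IRB | Deaths in the 30 days after study treatment, whatever the cause; other deaths at continuing review | Event-triggered. The 30-day rule is tied to receiving the drug, device or intervention, so it may not reach device-free controls equally. No discharge or stay data |
| 7.8.4.2, AE follow-up | AEs ongoing at withdrawal, outcome entered in the CRF | Ventilation is called completion and is not among the withdrawal reasons in 7.4.4. No discharge or stay data |
| 7.8.4.1, AE monitoring | Runs to the completion of follow-up | That endpoint is not defined |
| 7.12, discontinuation | Follow-up, where feasible, after stopping for safety or lack of effectiveness | Conditional; no content or timing |
| 7.10.1.6, AE tables | Tabulates deaths by arm | Reports deaths; does not collect them |
| 7.10.4, interim analysis | First 20 patients through hospitalisation | Describes a past analysis; sets no collection rule |

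These may return some or all later deaths. None systematically records discharge or length of stay after ventilation.

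**2. How large could it be?**

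Inputs: n = 30 per arm (Section 7.4.1). Assumed, because the documents give no values: ventilated share p = 0.10 to 0.30; share of ventilated patients later discharged alive q = 0.4 to 0.6. The share s of later vital statuses returned by safety reporting is unknown and is set at 0, 0.5 and 1.

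- Patients per arm with no scheduled record after ventilation, n × p: 30 × 0.10 = 3; 30 × 0.30 = 9. At a lower share of 3%, 30 × 0.03 = 0.9, about one patient.
- Width of the mortality bounds per arm (all unknown alive versus all unknown dead), p × (1 − s): s = 0 gives 10 to 30 points; s = 0.5 gives 5 to 15; s = 1 gives 0.
- Width for the difference between arms with equal p and s = 0, 2p: 20 to 60 points.
- Live discharges per arm with no scheduled record, n × p × q: 30 × 0.10 × 0.4 = 1.2; 30 × 0.30 × 0.6 = 5.4.

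The only mortality rate in the documents, 5.3% in Section 5.1, refers to confirmed cases rather than inpatients, so it is not used here. No figure is given for length of stay because its source is not defined.

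**Illustration of differential loss.** Assume 30% ventilated on control and 15% on active, mortality 30% to 50% after ventilation and 2% without it, nothing returned by safety reporting, and every survivor eventually discharged.

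- True mortality with 30% after ventilation: control 0.30 × 0.30 + 0.70 × 0.02 = 0.104; active 0.15 × 0.30 + 0.85 × 0.02 = 0.062; difference −4.2 points.
- True mortality with 50% after ventilation: 0.164 and 0.092; difference −7.2 points.
- Recorded mortality: 0.70 × 0.02 = 0.014 and 0.85 × 0.02 = 0.017; difference +0.3 points.
- Recorded live discharge: 0.70 × 0.98 = 0.686 and 0.85 × 0.98 = 0.833; difference +14.7 points, against a true +4.2 to +7.2.

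In this scenario a mortality benefit disappears while the live-discharge benefit is overstated. It shows that the distortion can matter and need not run one way; it does not predict the trial.

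The number affected also depends on what counts as mechanical ventilation. Section 6 lists noninvasive mechanical ventilation as such, while the daily log lists Bipap as an oxygen device. These passages must be reconciled.

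**The case against.** The strongest reply concerns mortality. Section 7.8.5 covers deaths in the 30-day window whatever the judged cause, with the rest at continuing review. Section 7.10.1.6 tabulates deaths by arm, and Section 7.10.1.1 puts every subject entering the study in the safety population. Section 7.2.1.1 also blurs completion with withdrawal, so AE follow-up under 7.8.4.2 might apply to a ventilated patient. This stands in part: mortality could turn out complete, which is why the bounds above go down to 0. But it rests on event-triggered reporting that may not treat the arms alike, and it does nothing for live discharge or length of stay.

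Second, Section 7.2.1.1 provides for EMR data to enter the CRFs, and admission and discharge dates are routine hospital data. The loss is thus probably recoverable. That is a reason the repair is cheap; the plan still does not schedule the abstraction.

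Third, Sections 7.10.1 and 7.10.1.3 defer detail to a separate SAP, and the CRFs and Data Management Plan are not available here. A derivation of length of stay may be in the SAP. An SAP cannot supply dates that were not collected.

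Fourth, Section 7.10.1.2 declares all comparisons nominal, and the primary safety measure in Section 7.7.3 is treatment-related SAEs. Both limit the seriousness; neither makes incomplete counts correct.

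Finally, the ventilation rates are assumptions, and entry criteria that admit saturation up to 96% could mean fewer ventilated patients. That is fair, and the 3% line shows the effect.

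**Conclusion.** The concern holds and should be fixed. Followed as written, the plan leaves live discharge and length of stay incomplete for every patient whose study ends at ventilation, and mortality possibly so. At an assumed 10% to 30% ventilated, that is 3 to 9 of 30 patients per arm. The resulting mortality uncertainty is 10 to 30 points per arm if no later status is recovered, 5 to 15 if half are, and none if all are. An estimated 1.2 to 5.4 live discharges per arm would have no scheduled record. The documents do not allow the size or direction of any difference between arms to be stated. Severity is moderate, because comparisons are descriptive and the primary safety measure does not depend on this follow-up.

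**What to change.** In Section 7.2.1.5, the synopsis and Table 1 footnote e, define end of device treatment and end of follow-up separately, leaving the rule for stopping device use as it is. Make the device protocol text in Section 7.2.1.1 consistent.

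For all randomised patients in both arms, subject to consent, abstract the following from the hospital record through actual hospital discharge or in-hospital death:

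- vital status and date;
- discharge date and destination.

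Include patients who have already completed. Define length of stay as admission to actual hospital discharge, with a stated rule for in-hospital deaths, unless the SAP already does so. Vital status at a fixed day and cumulative-incidence reporting are optional additions.

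The cost is a numbered amendment with written IRB agreement (Section 7.11) and abstraction of a few fields for up to 60 patients at the one hospital named in Section 7.4.1. Patients who have already completed need retrospective abstraction. There are no added visits or procedures. Whether existing consent covers data after study completion must be confirmed; the consent pages were not available for this review.
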